6.3.3.2. Month 2 (Visit 4) Procedures

- Record concomitant medications
- Count unused study drug tablets/ bottles/syringe and calculate compliance
- Dispense study drug medication and review dosing instructions
- Perform physical examination (see Section 9.10)
- Record vital signs (Section 9.9)
- Safety review for AEs/SAEs

- Review for endpoint events (VTE, bleeding)
 - The follow-up imaging performed if needed, must be always performed with the same modality as the initial diagnostic study

6.3.4. End of Main Treatment Period Visit (Month 3 or at least 6-12 weeks for Cohort 5, Visit 5) Procedures

All randomized subjects including those that have discontinued treatment will have an EOT assessment at Month 3 (within a ± 5 -day window).

The following will be performed at this visit:

- Perform physical examination (see Section [9.10](#))
- Vital signs (Section [9.9](#))
- Review concomitant medications
- Count unused study drug tablets/ bottles/syringe and calculate compliance
- Safety review for AEs/SAEs
- Review for endpoint events (VTE, bleeding)
 - Radiologic examination using the same diagnostic technique used at baseline to determine the thrombotic burden (see Section [7.1](#)).
 - VTE Radiologic Imaging (see Section [7.1](#)).
- Take samples for the following:
 - Liver function tests [ALT, AST, TBL, and ALP]
 - Serum creatinine
 - Hematology
 - Urine pregnancy test
- Dispense study drug medication and review dosing instructions per subject/parent's request and at the Investigator's decision to extend study treatment. After Month 3, the distribution of edoxaban or SOC may be for a 3-month period to align with the visit schedule, with the Sponsor's approval.

6.4. Extension Period (beyond Month 3 - Month 6, 9 and 12; Visits 6, 7, 8)

Per subject/parent's request and at the Investigator's decision, study treatment can be extended up to 12 months. At any time during the extended period, a subject can discontinue treatment and the study. In such a case a discontinuation study visit will be performed with a subsequent 30-day safety Follow-Up Visit (see [Table 17.1](#)).

The subjects on extended treatment will be followed for safety and efficacy assessment including bleeding events, recurrent VTE, and any treatment-related AEs at visit for Months 6 (Visit 6), 9 (Visit 7), and 12/ Discontinuation (Visit 8). Additionally, the subject will have a Follow-Up Visit (Visit 9) for safety assessment 30 days after treatment cessation. At Month

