	
• Spiral CT pulmonary angiography (CTPA)• Magnetic resonance pulmonary angiography (MRPA) 
Alternative imaging techniques:
 
• Cardiac angiography• Conventional pulmonary angiography• echocardiography
Sinovenous thrombosis	
• Brain MRI, including T2 imaging and MRI with venography (MRV)• Pre and post-contrast CT scan with venography (CTV) 
Alternative imaging techniques:
 
• Doppler flow US; if fontanelle open
Renal Vein thrombosis	
• US
Splanchnic and hepatic veins and vena cava	
• Doppler/US• CT/Scan

In certain cases, the use of 2 techniques may be required to objectively confirm the diagnosis of recurrent VTE. Further recommendations will be provided in the imaging manual but will be left for Investigator's discretion.

Diagnosis of fatal VTE is based on 1 or more of the following:

- Objective diagnostic testing
- Autopsy
- Death which cannot be attributed to a documented cause and for which VTE cannot be ruled out.

Thrombotic burden will be assessed by comparison of the diagnostic method used at baseline and at Month 3 \pm 5 days (for Cohort 5, at 6 to 12 weeks \pm 5 days) in the absence of symptomatic recurrent VTE. Hence, the same imaging technique that is used at the enrollment of the subject into the study will be required to be used at the end of the observational period \pm 3 days. A thrombotic burden endpoint will be registered if there is no regression of the thrombus size or extension of the thrombus at Month 3 visit \pm 3 days (for Cohort 5, at 6 to 12 weeks \pm 3 days) after randomization.

Additionally, thrombotic burden will be assessed at Month 12 \pm 5 days / Discontinuation Visit, for those subjects who participate in the Extension Period.

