11.4.1. Efficacy Analyses

11.4.1.1. Primary Efficacy Analyses

The primary efficacy analysis will be based on mITT Analysis Set. Analyses will be based on the randomized treatment arm even if a subject inadvertently receives the incorrect study drug. The primary efficacy endpoint is an event driven and a composite endpoint including symptomatic recurrent venous thromboembolic disease, death as result of VTE, and no change or extension of thrombotic burden from randomization to up to 3 months + 3 days from randomization. In this analysis, the time to the first event of the composite primary efficacy outcome will be analyzed using a Cox's proportional hazard regression model including treatment arm and age groups as covariates. Although this study is also stratified by region, region is not included in the model as a covariate because some age groups within regions may be very small due to the small overall sample size. The time to first event is defined as the time (days) from the day of randomization to the first event experienced by a subject during the 3 months + 3 days period. Subjects who did not have a primary efficacy outcome during the 3 months + 3 days period will be censored at 3 months + 3 days or the last day the subject had a complete assessment for study outcomes, whichever comes first. The edoxaban-to-comparator hazard ratio will be computed with 95% confidence interval (CI) (two-sided) based on this model. Edoxaban will be considered non-inferior to comparator if the upper limit of the 95% CI is ≤ 1.5 .

If non-inferiority of edoxaban is established, edoxaban will be tested for superiority to comparator. Edoxaban will be considered superior to comparator if the upper limit of the 95% CI from above analysis is ≤ 1.0 .

To control study-wise type I error, the testing for non-inferiority and superiority will follow the plan as described below.

The same proportional hazard model used for primary efficacy analysis will be performed for PP Analysis Set and Randomized Analysis Set as sensitivity analyses.

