**Samples taken as part of routine care outside the study requirements may be analyzed by local laboratories and the results used to qualify the subject provided the tests were performed for the newly diagnosed index VTE before randomization. If central laboratory is also used at the same visit with a resulting discrepancy for exclusion criteria, the local laboratory result will still be used to qualify the subject.

^a Randomization may occur in IXRS the day prior to dosing for clinical logistics.

^b Follow-Up Visit will be performed 1 month after the subject completes the study (6 weeks - Month 3 or Month 12 or 30 days after discontinuation from study in the extension period).

^c Scheduling of visits within windows should be done with caution to the drug supply available in a dispensing unit. PK/PD assessment on Day 5 cannot be performed before Day 5.

^d Targeted physical examination performed by an Investigator or other healthcare professional designated by the Investigator.

^e Vital signs include heart rate, body temperature, and sitting or supine blood pressure (Section 9.9).

^f INR assessment for adjustment of VKA dosages will be performed every month as per SOC. Additional interim evaluations may be performed at the discretion of the Investigator. INR will be assessed at Screening/Qualification visit if prior VKA was given or to be taken.

^g Investigator discretionary assessment of anti-FXa to be performed to determine if SP or LMWH are at therapeutic levels.

^h If image was taken for recurrent VTE after Month 3 but before discontinuation, then no image is needed at Month 12/Discontinuation. Optional Month 3 imaging can be done if recurrent VTE occurs prior to Month 3.

ⁱ Highly sensitive urine pregnancy test to be performed for females of childbearing potential.

^j AE/SAE reporting should occur throughout the study and not be restricted to specific visits.

^k Endpoint events should be reported as soon as site personnel learn of the event. Endpoint event should occur throughout the study and not be restricted to specific visits.

^l Prior medications includes 30 days prior to Screening/Qualification visit.

^m There is no dispensing or drug accountability requirement for Visit 2a for edoxaban arm for those subjects enrolled in the PK/PD evaluation because drug is expected to be dispensed on a monthly basis. The subject will need to bring in his/her edoxaban therapy for a single dosing treatment.

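### Section 11.4.1.1 has no dating rule for scan-detected outcomes, so the primary hazard ratio depends partly on when each arm is scanned

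*Combined protocol and SAP*

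**What the plan says.** - **Model.** Section 11.4.1.1: "the time to the first event of the composite primary efficacy outcome will be analyzed using a Cox's proportional hazard regression model", with treatment arm and age group as covariates. Non-inferiority is judged on the upper 95% limit against 1.5.
- **Event time.** "The time to first event is defined as the time (days) from the day of randomization to the first event experienced by a subject". Nothing separate is said about events found on a scheduled scan.
- **Censoring.** Event-free subjects are "censored at 3 months + 3 days or the last day the subject had a complete assessment for study outcomes", whichever is earlier. A complete assessment is not defined.
- **The scan component.** Section 7.1: "Thrombotic burden will be assessed by comparison of the diagnostic method used at baseline and at Month 3", and "A thrombotic burden endpoint will be registered if there is no regression of the thrombus size" or if the thrombus has extended. The same section gives both 5 days and 3 days either side for this comparison. Cohort 5 is scanned at 6 to 12 weeks.
- **The visit.** Section 6.3.4: "All randomized subjects including those that have discontinued treatment will have an EOT assessment at Month 3", with a window of 5 days either side. Table 17.1 schedules imaging at Screening, Month 3 and Month 12/Discontinuation only.
- **Dates in the analysis.** Section 11.2 rules out visit windows, so actual dates are used. No tie method, grouped-time model or interval-censored method is given for the primary endpoint.

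**The concern.** A Cox model compares, on each day, the share of each arm's at-risk subjects who have an event that day. For symptomatic recurrence or death, the event date says something about the disease. For the burden component, it says when the appointment fell. Suppose a failing scan is an event on its own date and a clear scan ends follow-up on its own date. The hazard inside the scan window is then

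P(scan fails) × P(scanned that day, given not yet scanned).

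The second factor has nothing to do with treatment effect. If one arm tends to be scanned later, its hazard is lower on every shared day, even when the same proportion fails. The trial is open-label and the visit may fall anywhere in a window of several days. The ratio tested against 1.5 could therefore move towards or away from non-inferiority for reasons of scheduling. This concerns scans that are done on time; missing scans are a different matter.

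**Working it through.** **1. The plan's own figures (Section 11.6).** Hazard ratio 0.76, margin 1.5, two-sided 0.05, 80% power, 1:1 allocation:

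- events = 4 × (1.960 + 0.842)² / [ln(0.76/1.5)]² = 67.9, so 68; power at 68 events is 80.0%;
- with arm rates of 28% and 0.76 × 28% = 21.28%, the mean is 24.64%, and 68 / 0.2464 = 276, against the stated 274.

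The sizing reproduces and is not in question.

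**2. Share of events found by scan.** Section 7.5 cites no-change rates of 14.8%, 17% and 18%; Section 11.6 expects a 28% composite. 14.8/28 = 53% and 18/28 = 64%. The plan does not state the share, so 50–80% was tried, with 50–60% as the main range.

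**3. Mechanism by hand.** Let scans be spread evenly over 11 days (nominal day ± 5), with one arm shifted 1 day later. On the nominal day the unshifted arm has 6 of 11 scan days left, so its daily scanning probability is 1/6. The later arm has 7 left, so 1/7. With equal failure risk, the ratio of event hazards that day is (1/7)/(1/6) = 0.86. Symptomatic events, unaffected by scan date, pull the overall estimate back towards 1.

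**4. Simulation.** Inputs: 28% failure in both arms (true ratio 1); nominal day 91; cut-off day 94 for 3 months + 3 days; whole days; Efron ties; 1,000,000 per arm. Scan-date spread is assumed: SD 2, 2.5 or 3 days, or uniform over 5 days either side. Edoxaban scans are shifted by 1 day. Each cell shows the hazard ratio for edoxaban 1 day later / 1 day earlier.

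| Spread | Censored at scan, share 50% | Censored at scan, share 60% | Censored at cut-off, share 50% | Censored at cut-off, share 60% |
|---|---|---|---|---|
| SD 2 | 0.821 / 1.208 | 0.788 / 1.261 | 0.959 / 1.028 | 0.941 / 1.031 |
| SD 2.5 | 0.849 / 1.177 | 0.816 / 1.220 | 0.954 / 1.033 | 0.938 / 1.049 |
| SD 3 | 0.871 / 1.149 | 0.842 / 1.182 | 0.949 / 1.039 | 0.936 / 1.052 |
| Uniform ± 5 | 0.878 / 1.166 | 0.849 / 1.205 | 0.941 / 1.059 | 0.925 / 1.079 |

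- *Censored at the scan date:* a shift of 12–26% at share 50–60%, and up to 37% at share 80%. At SD 2.5 and share 60%, ln(0.816)/ln(1.5) = −0.203/0.405, so 1 day is worth about half the margin on the log scale. Half a day gives about 0.90 and 2 days about 0.67.
- *Censored at 3 months + 3 days:* about 3–8% at share 50–60%, and up to 11% at share 80%. Most of it comes from scans on days +4 and +5 falling past the cut-off. If those scans also count, about 1–3% remains.

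**5. Effect on the decision.** In trials of 137 per arm with true ratio 1, scan-date censoring, SD 2–2.5 and share 60%, non-inferiority is met about 42–45% of the time with no shift. The figure is 71–79% if edoxaban is scanned 1 day later and 10–15% if 1 day earlier.

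**6. After the fix.** With all scan results, failing and clear, at day 91 and all in-window scans counted, a 1-day shift in either direction gives 0.996–1.005.

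**7. Why the tie method must be stated.** After the fix, most events share one day. In the limit where all do, the Breslow method returns the risk ratio. At a true hazard ratio of 1.5 and 28% control risk, the other arm's risk is 1 − 0.72^1.5 = 38.9%, and 38.9/28 = 1.39 rather than 1.5. That error favours non-inferiority.

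**The case against.** **The censoring date is open.** A reader might infer that clear subjects are certainly censored at the scan. The text does not say so. Visit 9 reviews VTE and bleeding 30 days after Month 3 (Section 6.5). If that counts as a complete assessment, completers are censored at 3 months + 3 days. Section 11.4.1.2 uses the same phrase with a limit of last dose + 30 days, which would seldom bind if a scan were required. On the other side, Visit 9 has no imaging and may be a phone call, which fits poorly with a complete assessment of an endpoint that includes imaging. Both readings are tenable, so both sizes are given.

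**No difference between arms is shown.** A reader might also infer serious inflation of false non-inferiority. At a true ratio of 1.5, scans within 3 days and scan-date censoring, simulation gives 28% and 75% for edoxaban scanned 1 and 2 days later, against a nominal 2.5%. Those figures need a systematic delay that the documents do not show:

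- Chance is not enough. The standard error of the difference in mean scan day is SD × √(2/137): 2.0 × 0.121 = 0.24 days for whole days evenly spread over ± 3, or 3.16 × 0.121 = 0.38 for ± 5. One day is about 2.6 to 4 standard errors.
- Footnote c of Table 17.1 ("Scheduling of visits within windows should be done with caution to the drug supply available in a dispensing unit") would, if anything, discourage late edoxaban visits, which raises the ratio. Section 5.2.4 supplies overage, and centrally sourced comparator is also dispensed through IXRS.
- IXRS issues a calendar of visit dates (Section 5.1.2).
- The opposite direction is possible too. Section 6.3 counts months of treatment while the analysis clock starts at randomization, and Section 5.1.1 describes delayed starts for some edoxaban subjects.

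**Partly visible already.** Section 11.4.1.2 tabulates each component by arm, so a ratio produced by timing alone would sit beside similar proportions. Section 11.7 leaves definitions to a SAP finalised before database lock. The rule could be set there, but the text supplied contains none.

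What stands is that the size is conditional and the direction unknown. The dependence of the primary ratio on scan dates is not answered.

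**Conclusion.** The point holds in conditional form. Followed as written, Sections 11.2 and 11.4.1.1 let appointment dates enter the primary hazard ratio through the component that probably supplies more than half the events. A 1-day difference in mean scan date moves the ratio by roughly 12–26% if clear subjects are censored at the scan (share 50–60%), and by about 3–11% if censored at 3 months + 3 days (share 50–80%). One undefined phrase decides which applies.

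These sizes rest on an assumed scan-date spread and on a scan share inferred from cited rates. Dropout, age cohorts and Cohort 5 were not modelled; scans anywhere from 6 to 12 weeks make the dating question wider there. It is a risk to remove before database lock, not evidence of bias in a known direction. It does not call for replacing the Cox model: a binomial model in its place would leave subjects censored before the scan without a direct place, and a dating rule alone removes the artefact.

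**What to change.** In Section 11.4.1.1:

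- Assign every in-window end-of-period scan result, failing or clear, to one nominal time: Month 3, or for Cohort 5 the nominal week of the planned scan. State one scan window, since Section 7.1 gives two.
- State that event-free subjects with that scan are censored at the same nominal time, so that scans on days +4 and +5 are not lost to the cut-off.
- Keep actual dates for symptomatic recurrence and death.
- Keep the Cox model and the 1.5 margin, and name the tie method (Efron, for example).
- Add two sensitivity analyses: the Cox model on actual dates, and a complementary log-log or risk-ratio analysis. Tabulate scan day by arm.

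The cost is a few sentences of protocol and SAP text. No new data or subjects are needed, and the 68-event sizing stays. The downside is that timing of scan results within the window is no longer used.

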11.4.1.2. Secondary Efficacy Analyses

The following secondary efficacy analyses will be conducted:

- A composite endpoint, including symptomatic recurrent venous thromboembolic disease, death as result of VTE, and no change or extension of thrombotic burden from the randomization to the date of the last dose of study drug + 30 days, the same Cox proportional hazards regression model used for the primary efficacy analysis will be used. The time to first event is defined as the time (days) from the day of randomization to the first event experienced by a subject from the randomization to the date of the last dose of study drug + 30 days. Subjects who did not have a primary efficacy outcome during the study period will be censored at the last day the subject had a complete assessment for study outcomes or the last study drug + 30 days, whichever came first. These efficacy analyses will be based on mITT and PP Analysis Sets. The incidence of this composite endpoint will also be summarized by treatment arm for the mITT and PP Analysis Sets.
- Incidence of all-cause mortality from randomization to the date of the last dose of study drug + 30 days will also be summarized by treatment arm for the mITT Analysis Set.
- The incidence of each component (symptomatic recurrent venous thromboembolic disease, death as result of VTE, and no change or extension of thrombotic burden) of the composite primary endpoint occurred during the first 3 month treatment period will be summarized by treatment arm for the mITT and PP Analysis Sets.

- The occurrence of DVT, catheter-related thrombosis, sinovenous thrombosis, and PE during the first 3-month treatment period, after the 3 month treatment period will be summarized by treatment arm for the mITT Analysis Set

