5.6.1. Discontinuation from Treatment within the Main Treatment Period (Month 3)

Early discontinuation of study drug is discouraged. However if, in the Investigator's opinion, continuation of study drug would be detrimental to the subject's well-being or in specific clinical situations (eg, liver function test disturbances, severe renal insufficiency, recurrent VTE, bleeding), the study drug can be stopped permanently. Subjects who discontinue treatment during the Main Treatment Period should return to the clinical site per the study procedure schedule (Table 17.1) for all remaining safety and efficacy assessments through the scheduled Month 3 visit (Visit 5) regardless of what treatment, if any, they may subsequently be taking. A 30-day Follow-Up Visit (Visit 9) will be required for all subjects completing Month 3, regardless of discontinuation from treatment during the main treatment period. If a subject discontinues study medication before Month 2, the follow up visit may be combined with Month 3 Visit.

A telephone call for follow-up assessment may be conducted in exceptional circumstances when the subject is not able or willing to present to the study center.

The reasons for discontinuation from treatment must be documented.

If a subject discontinues study treatment prior to Month 3, the Investigator will complete and report the observations as thoroughly as possible at scheduled visits including the date of last treatment and the reason for discontinuation of study treatment through 3 months of observation.

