11.2. General Statistical Considerations

All efficacy analyses will be based on the mITT Analysis Set or PP Analysis Set and will be performed based on the treatment arm assigned at randomization. All statistical tests will be two-sided at a 5% significance level, unless otherwise specified.

Safety analysis will be performed using the Safety Analysis Set. Subjects will be analyzed according to actual treatment received.

Unless otherwise specified, the baseline value of an efficacy variable for a subject is the last non-missing measurement before the first administration of study drug, and the baseline value of a safety variable is the last non-missing measurement before the first dose of the study drug.

In general, missing data will not be imputed for the purpose of data analysis. No visit windows will be used for analysis.

Continuous variables will be summarized by the number of observations, mean, standard deviation, median, and minimum and maximum values. Categorical variables will be summarized using frequency counts and percentages. Summary statistics will be presented by treatment arm.

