11.6. Sample Size Determination

This is an event driven trial and the total number of subjects randomized to treatment may be adjusted to ensure accumulation of 68 events in the mITT Analysis Set during the Main Treatment Period.

The sample size calculation is based on statistical approach and results of Hokusai VTE study (DU176b-D-U305), a study of LMWH/edoxaban versus LMWH/warfarin in the treatment of acute VTE in adults. An NI margin of 1.5 (in hazard ratio) is used in the Hokusai VTE study and was aimed at preserving 70% of warfarin effect in adult population. A hazard ratio of 0.76 of recurrent VTE between edoxaban and warfarin for the first 3 months is also observed in Hokusai VTE study.

This pediatric study is designed to accumulate, approximately 68 overall primary efficacy events in the mITT Analysis Set during the Main Treatment Period. Assuming that edoxaban group will observe a 24% relative reduction to SOC arm, a total of 68 events will give approximately a power of 80% to demonstrate that LMWH/edoxaban is non-inferior to the comparator, considering a relative non-inferiority margin for the hazard ratio of 1.5 (two-sided $\alpha=0.05$).

Based on the completed clinical trials and literature review^{4, 14, 15, 16, 19, 22, 23, 24, 25}, we expect an incidence of composite primary efficacy endpoint of 28% in the control arm during the Main Treatment Period. Based on these estimates, 274 subjects (137 each arm) are expected to be randomized to study drug in order to accrue 68 primary efficacy events in the mITT Analysis Set during the Main Treatment Period.

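### The secondary composite and all-cause mortality windows end at last dose + 30 days, so early stoppers' Month 3 scans and later deaths go uncounted in those two analyses

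*Combined protocol and SAP*

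**What the plan says.** Section 11.4.1.2 analyses the secondary composite with the primary Cox model, timing it to the "first event experienced by a subject from the randomization to the date of the last dose of study drug + 30 days". Event-free subjects are censored at that date or at their last complete outcome assessment, whichever is earlier. The analysis sets are mITT and PP, and incidence is also tabulated by arm. The same section summarizes "Incidence of all-cause mortality from randomization to the date of the last dose of study drug + 30 days" by arm in mITT, with no test or model. The Synopsis, Section 2.1.2 and Section 7.2 give the same end date for both endpoints.

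Follow-up does not end with the drug:

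- Section 5.6.1 has subjects who stop in the Main Treatment Period return "for all remaining safety and efficacy assessments through the scheduled Month 3 visit (Visit 5").
- Section 6.3.4 requires the Month 3 assessment, which includes the repeat scan, in every randomized subject, on or off treatment.
- Section 6.3.3 continues endpoint and SAE follow-up to Month 3.
- Section 6.5.1 puts the follow-up visit 30 days after Month 3. Section 5.6.1 lets it be merged with Month 3 when drug stops before Month 2.
- Section 15.10 sends all deaths, and suspected endpoints after permanent discontinuation, to blinded adjudication.

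The primary analysis (Section 11.4.1.1) counts events to 3 months + 3 days from randomization whatever the treatment status.

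**The concern.** The secondary composite is presented as the longer version of the primary endpoint. For an early stopper it is the shorter one, and its length is set by an event after randomization. The largest planned source of information on thrombotic burden, the Month 3 scan, then lies outside the window although it has been taken and adjudicated. Deaths after the cut-off are treated the same way.

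Treatment is open-label, and the reasons for stopping in Section 5.6.3 include adverse events and lack of efficacy. If early stopping differs between arms, the incidence tables no longer compare like with like. If stopping is also related to outcome, the hazard ratio can be affected. Neither endpoint has a sensitivity analysis with a fixed window.

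**Working it through.** **1. The plan's own figure.** The inputs, from Sections 11.2 and 11.6, are:

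- "All statistical tests will be two-sided at a 5% significance level, unless otherwise specified"
- "Assuming that edoxaban group will observe a 24% relative reduction to SOC arm"
- "considering a relative non-inferiority margin for the hazard ratio of 1.5"
- "we expect an incidence of composite primary efficacy endpoint of 28% in the control arm during the Main Treatment Period"

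Schoenfeld's formula for non-inferiority gives D = 4 × (1.960 + 0.842)² / [ln(0.76/1.5)]² = 67.9, rounded up to 68. Power at 68 events is 0.800. This agrees with Section 11.6, where "a total of 68 events will give approximately a power of 80" percent.

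For N, a 24% reduction in risk gives 28% × 0.76 = 21.3% and 68 / 0.2464 = 276. A hazard ratio of 0.76 gives 1 − 0.72^0.76 = 22.1% and 272. The planned 274 lies between them. These figures belong to the primary endpoint, whose window does not depend on last dose, so nothing here changes them.

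**2. Dates.** Take Month 3 as Day 90. The visit window of ±5 days makes it Day 85 to 95. The scan is inside the secondary window only if last dose + 30 ≥ scan day, so last dose must be on or after Day 60 (Day 55 to 65 across the visit window).

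| Last dose | Window closes | Days before Day 90 scan | Days before Day 120 contact |
|---|---|---|---|
| Day 14 | Day 44 | 46 | 76 |
| Day 30 | Day 60 | 30 | 60 |
| Day 45 | Day 75 | 15 | 45 |
| Day 60 | Day 90 | 0 | 30 |
| Day 75 | Day 105 | 0 | 15 |

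The last column is the uncounted period for deaths when the follow-up visit is held 30 days after Month 3. If that visit is merged with Month 3, the third column applies instead.

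**3. Scan events lost.** The documents give no early-stop rate, so 5%, 10% and 20% are assumptions. Section 7.5 cites 14.8% to 18% for unchanged burden. Per Section 1.1 those studies had varied and often long follow-up, so applying the rate at Month 3 is also an assumption. Events lost = 274 × stop rate × burden rate.

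| Stop before Day 60 | Subjects | Scan events lost | As a share of 68 |
|---|---|---|---|
| 5% | 13.7 | 2.0 to 2.5 | 3.0% to 3.6% |
| 10% | 27.4 | 4.1 to 4.9 | 6.0% to 7.3% |
| 20% | 54.8 | 8.1 to 9.9 | 11.9% to 14.5% |

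At these rates the counts are an upper bound, because Cohort 5 scans may be taken at discontinuation (Table 17.1, footnote n) and so fall inside the window. The 68 is the primary event count and serves only as a yardstick.

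**4. Crude incidence.** Suppose there is no true difference, a 28% composite in both arms, and all non-scan events inside the window. Let early stopping be 15% on edoxaban and 5% on SOC.

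- Burden rate 18%: (0.10 + 0.85 × 0.18) / (0.10 + 0.95 × 0.18) = 0.253 / 0.271 = 0.93.
- Burden rate 14.8%: (0.132 + 0.85 × 0.148) / (0.132 + 0.95 × 0.148) = 0.2578 / 0.2726 = 0.95.

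At 20% against 5%, the ratios are 0.90 and 0.92. The true ratio is 1.00 throughout.

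**5. Cox model.** Censoring stoppers does not shift the hazard ratio if their risk equals that of subjects still in the window. If stoppers fail the scan at twice the 18% rate, the full-follow-up incidence ratio at 15% against 5% is (0.10 + 0.85 × 0.18 + 0.15 × 0.36) / (0.10 + 0.95 × 0.18 + 0.05 × 0.36) = 0.307 / 0.289 = 1.06. At 20% against 5% it is 0.316 / 0.289 = 1.09. Among subjects still in the window, the comparison at the scan stays at 1.0. If stoppers fail at half the rate, the 15% against 5% ratio becomes (0.10 + 0.153 + 0.0135) / (0.10 + 0.171 + 0.0045) = 0.2665 / 0.2755 = 0.97. The direction of any bias therefore depends on why subjects stop.

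**The case against.** The strongest reply is that the window is deliberate. It is the same in the objectives, endpoints and analysis, and it matches the + 30 days used for bleeding, for net clinical outcome (Sections 11.4.1.4 and 11.4.3.1) and for adverse-event recording (Section 9.1). A primary analysis that ignores stopping, paired with a secondary one tied to exposure, is a legitimate design. This stands as far as it goes, and it is the reason to keep the current window as one version. But the plan gives no rationale, and it analyses these as efficacy endpoints in mITT by randomized arm.

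It is also right that little is lost from the trial as a whole. A reader might infer that early stoppers' scans are discarded. They are not: the primary analysis and the three-month component summaries keep them, as well as VTE deaths in that period. A late non-VTE death has no efficacy analysis, although Section 11.4.3.2 tabulates deaths under safety.

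A reader might further infer that the window censors the subjects most likely to fail or die, and so biases both comparisons toward the arm with more stopping. The documents do not establish this. The first reason for stopping in Section 5.6.3 is that anticoagulation is no longer needed, which may mark a good outcome. A subject who stops because of recurrent VTE already has the event. Mortality is only summarized.

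Finally, one could assume that 30% of stoppers fail the scan and reach 274 × 0.20 × 0.30 = 16 events. The documents have no source for that rate.

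**Conclusion.** The point holds in a limited form. Outside Cohort 5, a last dose before about Day 60 puts the required Month 3 scan beyond the secondary composite's window. The nominally longer endpoint can then hold fewer events than the primary one. It need not, since it also gains extension-period events and Month 12 scans. Deaths from last dose + 30 days to the end of follow-up (about Day 90 with a merged visit, otherwise about Day 120) are missing from the mortality summary.

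The size is at most about 2 to 2.5, 4 to 5 or 8 to 10 scan events for assumed early-stop rates of 5%, 10% or 20% and a burden-failure rate of 14.8% to 18%. Unequal stopping lowers crude incidence mechanically in the arm that stops more. Hazard-ratio bias is conditional on stoppers' risk and could go either way.

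Stops after about Day 60 keep their scans, withdrawn subjects have no later data to lose, and after Month 3 follow-up itself ends about 30 days after discontinuation. The non-inferiority conclusion, the 68 events and the 274 subjects are untouched. The change is worth making because the data are already collected.

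**What to change.** 1. **Secondary composite.** Run the window from randomization to the later of (a) the end of the primary window, Month 3 + 3 days or the end of the Cohort 5 period, and (b) last dose + 30 days. State that the Month 3 scan counts, because a visit window of ±5 days can place it just after + 3 days. Change the censoring rule to match.
2. **All-cause mortality.** Summarize deaths over a fixed window from randomization through Month 3 + 3 days in all mITT subjects. Report deaths to last study contact as supportive only: participation runs from 4 to 13 months (Synopsis), so that count still varies with treatment duration.
3. **Current window.** Keep last dose + 30 days for both endpoints, labelled as the on-treatment version.

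The cost is one additional analysis per endpoint and aligned wording in the Synopsis and Sections 2.1.2, 7.2 and 11.4.1.2. No new data or visits are needed. After Month 3 the composite window still depends on treatment duration, which the text should acknowledge.
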